A Randomized Control Trial Treating Depression With Yoga and Coherent Breathing Versus Walking in Veterans

NCT03489122

Document Date: 3-20-2017

D.17. Data Management and Analysis Plan: The Data Coordinating Center at the Boston University School of Public Health will provide data management, including the development and maintenance of a REDCap database and the creation of a final database that will be sent to [name] for statistical analysis, using SPSS 23.0. Descriptive statistics will be generated for baseline data and distributions between the yoga intervention and walking intervention will be compared using two-sample t-tests and chi-square or Fisher's exact tests to assess effectiveness of randomization. Descriptive statistics include means and standard deviations for continuous variables and group sizes and proportions for categorical variables. All analyses will be performed at the $\alpha = 0.05$ level of significance. Should groups have unequal distributions at baseline, relevant variables will be incorporated in subsequent linear models that will be used to examine intervention efficacy. In order to address the study aims of assessing the relative longitudinal change in dependent variables between yoga intervention and walking intervention groups over time, data will be collected at four time points, pre-randomization, and at weeks 4, 8, and 12. Mixed linear model analyses will be performed focusing on the group x time interaction for the primary effects to be statistically modeled. These analyses will allow for inclusion of data at differing numbers of time points per subject if needed. We will examine different within-subject correlation structures for our interaction model and determine the optimal structure by comparing Akaike information criteria (AIC) values. The correlation structure that yields the lowest AIC will be adopted. Subjects who change antidepressant medications during the study will be included in intent to treat analysis, but will be co-varied for medication changes. Potential cohort effects will be statistically addressed by controlling for group profiles, including group size, breakdown by sex of attendees, instructor, group parameters such as individual or group sessions, and group cohesion/overlap.

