3.0 RESEARCH DESIGN AND METHODS

3.1 Drug/Device Information: NOT APPLICABLE

3.2 Type of Study: (Table 3: Individual Timeline): This is a longitudinal, efficacy randomized controlled trial (RCT). Veterans with MDD will be evaluated for eligibility and randomized to a 12-week intervention of a twice-weekly yoga and coherent breathing or walking group. As there is evidence that exercise improves mood in unipolar depression, the walking group will serve as an active control condition.(47) The policy for Common Data Elements will be incorporated into the data collection matrix. The Consolidated Standard of Reporting Trials (CONSORT) will be used to ensure the quality of reporting for this RCT.(48) The **primary dependent variable** will be changes in the Hamilton Depression Rating Scale (covering a 2 week period), and mood and anxiety scales (designed for repeated use, such that changes from pre to post intervention can be gauged), measured using valid and reliable psychological instruments obtained at screening, intervention weeks 4, 8, and 12, and before each MRS scan. The **secondary dependent variable** will be brain gamma amino-butyric acid (GABA) levels measured by magnetic resonance spectroscopy (MRS) in the left thalamus, the same region used in our prior studies.(9, 53, 65) The thalamus has the technical advantage of providing high quality spectra, has a high concentration of GABAergic neurons, and thus a high GABA signal, in which changes can be detected. The thalamus is also anatomically connected to other regions of interest. GABA levels will be measured by MRS in 3 separate scan acquisitions: before randomization (Scan 1), after 12-weeks of the yoga or walking intervention (Scan 2), followed immediately by the group assigned intervention and the final scan (Scan 3). The **third dependent variable** will be respiratory sinus arrhythmia (RSA) a component of heart rate variability (HRV) that is an accurate index of vagal influences on the heart.RSA will be measured before each scan and before and after an intervention at week 4, week 8 and week 12. Medications also are evaluated at weeks 4, 8, and 12. Two and six month follow-up phone calls will assess depression, quantity of yoga practice, and barriers to practice.

3.3.1. Sub-Study Participation: This is not a multisite study. There will be a contract with the McLean Hospital for goods and services regarding the imaging component of this study.

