3.4. Data Collection

3.4.1. Discussion of VA research activities and data for non-VA research activities and non-VA data: All activities conducted under this study are for research purposes. The VABHCS is the coordinating center through which all recruitment, advertisements, participant assessments, and interventions associated with this research project will occur with the following exceptions. There will be a contract with the McLean Hospital for the acquisition, and analysis of the MRI data. There will be a contract with [name] for the analysis of the ECG data. The contracts and agreements will clearly state that the data acquired and analyzed are good and services and belong to the VA.

3.4.2. Data collection, storage, access, use, disclosure, and analysis:

3.4.2.1. Describe all data collection activities for VA research:

The collection of imaging data at the McLean Hospital was approved by VACO. There are three dependent variables: 1) Hamilton Depression Rating Scales, 2) Thalamic GABA levels, and 3) Respiratory Sinus Arrhythmia (RSA).

3.4.2.1. Psychological Scales: All data from screening and intervention assessments will take place at the VABHCS and will be put into REDCap. Evaluations at the McLean Hospital will be put into REDCap using a VA issued laptop.

3.4.2.2. Spectroscopic Data: All magnetic resonance imaging (MRI) and magnetic resonance spectroscopy (MRS) data used for analysis of GABA levels will be collected and analyzed at the McLean Hospital under a contract that will state that the data collected under the contract belongs to the VABHCS. The analyzed data will be transferred via secure electronic means for incorporation in the final data set. All individuals scanned at the McLean Hospital are checked in using their name, address and social security number.

3.4.2.3. Formal Reading of MRI Study: It is the policy of the McLean Hospital that all research subjects have a VA brain scanning sequence that is formally read by a person qualified to read MRI studies. This formal reading does have the subject name on it. The data that will be used for the study will only be marked with the subject ID.

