3.5.1. Data Management: The study statistician will provide leadership and expertise in data collection, management and analyses, encompassing database design, implementation of quality control procedures, technical support, and data sharing. A close interaction between data management staff and research team members will result in procedural consistency, efficiency of the study-wide systems, and ultimately produce the highest quality data. Data collection strategies will include web-based assessments using VA REDCap software. When possible, data will be collected on desktop computers, or laptops, negating the need for double entry. Electronic forms will include required fields, skip patterns, and validation resulting in more complete and "cleaner" data at capture. All participants will be assigned a unique identifier (ID) and personal identifiers that must be collected and used for consent and follow up will be stored in a separate database apart from study data. Analysed data from McLean Hospital and [name] will be provided via a VA approved system (e.g., AZURE)

3.5.1. Analysis of Hypotheses (Aim 1: Hypotheses 1. Aim 2: Hypotheses 2. Aim 3: Hypothesis 3)

Hypothesis 1. a. Depressive Symptoms: The yoga group will have decreased depressive symptoms compared to the walking group. There will be a significant within-group change (decrease) in

depressive symptoms over time, using a mixed linear model analogue of repeated measures analysis-of-variance with independent groups in MDD subjects assigned to the yoga group.

Hypothesis 1. b. Mood Scales: There will be a greater improvement in mood (as measured by the EIFI and STAI), and sleep (as measured by the PSQI) in the yoga group compared to the walking group.

Hypothesis 2. a. GABA: GABA levels will increase in the yoga group. There will be a within-group change in GABA levels over time using a mixed linear model analogue of repeated measures analysis-of-variance with independent groups in MDD subjects assigned to the yoga group.

Hypothesis 2. b. Group Differences: There will be a between-group difference in GABA levels over time using linear modeling comparing the yoga group with the walking group.

Hypothesis 3. a. RSA: There will be tonic increase in post intervention recovery RSA in the yoga but not the walking group.

Hypothesis 3. b.: There will be an increase (from baseline to end of week 12) in the difference between pre- and post-intervention in the rest and the recovery RSA in the yoga group.

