Hypothesis 4. a. Exploratory Concurrent Antidepressants: The yoga group but not the walking group will have a decrease in depressive symptoms regardless of antidepressant treatment at the beginning of the study.

Hypothesis 4. b. Exploratory PTSD Symptoms: If PTSD symptoms are present at screening, there will be a greater decrease in PTSD symptoms in the yoga compared to the walking group as measured by CAPS and PCL-C.

Hypothesis 4. c. Resting State Connectivity will increase over the course of the study with greater increases in the yoga group.

Hypothesis 4. d. Executive Function will increase over the study as measured by the Stroop, Digit Symbol test and fMRI activation.

3.5.2. Power Analysis for Depressive symptoms and Mood Scales: Based on the power analyses below, in order to achieve adequate power for all analyses, n=70 subjects, n=35 in the yoga and n=35 in the walking intervention must complete the interventions. Using Study 4 data in subjects with MDD in the LDG, the repeated measures ANOVA for EIFI scores from screening to the completion of the intervention did not reach statistical significance in the group of n=15 (baseline: 3.1 ± 2.2 and week-12: 3.9 ± 2.7 , $F_{1,13} = 1.097$, $p = 0.31$), a post hoc power analysis was conducted, which determined that the achieved effect size was $f = .281$, with 52% power. Based on this same effect size, an a priori power calculation was conducted, which determined that **n=35** subjects would be needed to detect significant differences for BDI-II, STAI, and EIFI scores from screening to the completion of the intervention, with effect size $f = .281$, with $< = .02$ to account for multiple comparisons, and 81% power. As the power analysis for the EIFI requires the largest number of subjects (n=70), which will be used to determine sample size. In order for 70 subjects to complete the intervention, assuming a 20% drop out, 84 subjects will be randomized.

3.5.3. Power Analysis for GABA: Consistent with our analytic plan for the longitudinal questions at-hand, we can compute the statistical power for Hypothesis II an analysis sample of **n=26** subjects in each of the study groups using the mixed linear model analogue of repeated measures analysis-of-

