variance with independent groups. We used nQuery Advisor, version 7.0 for these computations. Using GABA level as the dependent variable of interest and employing the observation from Study 2 in which the walking intervention showed no change in GABA over the 12-week intervention, it is predicted that GABA levels will not change over time in the walking group. We hypothesize that the yoga group will show mean GABA/Cr = 0.28, 0.285, and 0.32 at the three study time points and that the walking group will show mean GABA/Cr = 0.28, 0.28, and 0.28. Assuming a common standard deviation at each time point of 0.06 and a within-subject correlation of 0.65, we will have 80% power to detect the above noted pattern of repeated mean GABA/Cr with a two-sided alpha of 0.05. With the same data configuration, we will have 85% power should the within-subject correlation be as high as 0.70.

3.5.4. Tonic changes in Recovery RSA from screening to 12 weeks: The GEE of changes in recovery RSA in the full cohort (n=27) over 12 weeks was significant in Study 4; however, only the recovery RSA values in the smaller LDG (n=14) were used for the power analysis, as this reflects the dosage that will be utilized in the proposed study. While the repeated measures ANOVA did not reach statistical significance in the LDG (screening mean = 7.7 ± 2.5 and 12 week mean = 8.2 ± 2.9 , $F_{1,12} = 1.094$, $p = 0.315$), a post hoc power analysis was conducted, which determined that the achieved effect size was $f = 0.291$, with 52% power. Based on this same small to medium effect size, an a priori power calculation that includes two groups (yoga and walking) was conducted, which determined that **n=34** subjects would be necessary to detect significant differences in RSA at effect size $f = 0.291$, with 90% power.

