3.5.5. Acute changes in RSA at 12 weeks (pre and post yoga intervention): Half way through Study 4, an RSA collection was added prior to the 12-week yoga intervention, which allowed acute changes in RSA to be calculated. An ANOVA of rest stage changes reached statistical significance; 12-week pre intervention resting mean = 4.9 ± 1.8 and 12-week post intervention resting mean = 5.7 ± 1.6 ($F_{1,14} = 11.056$, $p = .005$). A post hoc power analysis was conducted, which determined that the achieved effect size was $f = .858$, with 99% power. Based on this same large effect size, an a priori power calculation was conducted, which determined that **n=10** subjects would detect significant differences at effect size $f = .858$, with alpha = .01 and two groups (yoga and walking) would achieve 90% power. An ANOVA of rest stage changes reached statistical significance; 12 week pre intervention recovery mean = 6.7 ± 2.4 and 12 week post intervention recovery mean = 8.1 ± 3.4 ($F = 3.819$, $p = 0.070$). A post hoc power analysis was conducted, which determined that the achieved effect size was $f = 0.504$, with 96% power. Based on this same large effect size, an a priori power calculation was conducted, which determined that **n=20** subjects would detect significant differences at effect size $f = 0.504$, with $\alpha = .01$ and two groups (yoga and walking) would achieve 90% power.

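### Aim 1 is sized at .02 to allow for multiple scales, but the SAP and protocol test everything at 0.05 with no procedure or success rule, and the primary is an open bundle

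*SAP*

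**What the plan says.** **Analysis level.** SAP D.17: "All analyses will be performed at the $\alpha = 0.05$ level of significance". Protocol 3.5.1 (Data Management and Analysis Plan) has the same sentence. Both plan a mixed linear model over four time points, focused on the group-by-time interaction. Neither names a multiplicity procedure, a testing order or a success rule.

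**Levels used for sizing.**
- Aim 1 (protocol 3.5.2): 35 "subjects would be needed to detect significant differences for BDI-II, STAI, and EIFI scores from screening to the completion of the intervention", with f = .281, "with $< = .02$ to account for multiple comparisons, and 81% power".
- GABA (3.5.3): "we will have 80% power to detect the above noted pattern of repeated mean GABA/Cr with a two-sided alpha of 0.05".
- Tonic RSA (3.5.4): no level given.
- Acute RSA (3.5.5): the rest-stage contrast is sized "with alpha = .01 and two groups (yoga and walking) would achieve 90% power", and the recovery-stage contrast also uses .01.

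**Primary.** Protocol 3.2 says the primary dependent variable "will be changes in the Hamilton Depression Rating Scale (covering a 2 week period), and mood and anxiety scales". Protocol 3.4.2.1 says "There are three dependent variables: 1) Hamilton Depression Rating Scales, 2) Thalamic GABA levels, and 3) Respiratory Sinus Arrhythmia (RSA"), without calling any of them primary. Hypothesis 1.b adds: "There will be a greater improvement in mood (as measured by the EIFI and STAI), and sleep (as measured by the PSQI"). HDRS has no power calculation anywhere.

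**The concern.** Section 3.5.2 recognises that several Aim 1 scales will be tested and lowers the level to allow for it. The analysis section does not carry that through. Followed literally, each scale is tested at 0.05, and the protection assumed in the sample size disappears.

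The loose primary makes this matter. Section 3.2 bundles HDRS with scales it does not list, and no success rule is given. The documents therefore do not say whether a null HDRS with a positive EIFI or STAI would support Hypothesis I. That could be decided after the results are seen.

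**Working it through.** **1. Confirm that .02 is a significance level.** The symbol before the equals sign in 3.5.2 is garbled in the extracted text, so I reproduced the stated power.
- From 3.5.2: n = 35, f = .281, stated power 81%. Assumed: two measurements (m = 2) and within-subject correlation ρ = 0.5, which the documents do not give.
- Noncentrality λ = n·m·f²/(1 − ρ) = 35 × 2 × 0.281² / 0.5 = 11.05, with F on 1 and 34 df.
- Power is 80.6% at .02 and 89.8% at .05.
- The same formula at n = 15 and .05 gives 52.7%, against the stated post hoc 52%.

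The stated 81% matches .02, so that was the level used.

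**2. False-positive chance if any one of the three sized scales counts.** For independent tests, 1 − (1 − α)³:
- α = 0.05: 1 − 0.95³ = 14.3%
- α = .02: 1 − 0.98³ = 5.9%

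For equally correlated two-sided normal tests, by numerical integration (correlations assumed):

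| Correlation | Three at 0.05 | Three at .02 | HDRS added, four at 0.05 |
|---|---|---|---|
| 0 | 14.3% | 5.9% | 18.5% |
| 0.7 | 10.9% | 4.7% | 13.0% |
| 0.9 | 8.4% | 3.5% | 9.4% |

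With HDRS as sole primary the figure is 5%. Protocol 3.3.2.1 gives EIFI four subscales. Counting them separately makes six tests without HDRS, and 26.5% (correlation 0) to 10.8% (0.9) at 0.05.

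**3. Acute RSA.** Same formula with two groups and ρ = 0.5. For 90% power at .01 the smallest totals are 9 (f = .858) and 19 (f = .504), against the stated 10 and 20. At .05 they would be 7 and 13. So .01 was the level used, and both totals lie far below the planned 70 completers.

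**4. What f = .281 represents.** Section 3.5.2 takes it from a yoga-only change with F = 1.097 on 1 and 13 df.
- The square root of 1.097/15, 1.097/14 and 1.097/13 is 0.27, 0.28 and 0.29. So .281 is about the standardized change itself and already contains the within-subject correlation.
- Putting .281 into the step 1 formula at n = 15 gives λ = 15 × 2 × 0.281² / 0.5 = 4.74. That implies an F of about 4.7, not the reported 1.097. Step 1 therefore identifies the level used but does not validate f.
- Take a yoga change of 0.27 to 0.29 standard deviations of change, no change in walking, equal variances and 35 per arm. The noncentrality of the two-sample t-test is 0.27 × √(35/2) = 1.13 to 0.29 × √(35/2) = 1.21, on 68 df.
- Power is about 20% to 22% at .05 and 11% to 13% at .02.

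This last result is a two-measurement approximation, not the planned four-time-point mixed model.

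**The case against.** **The two levels can be read together.** The .02 is close to .05/3 = .0167, so 0.05 could be the overall level and .02 the per-scale level. That reading is possible, and it is why the documents do not show a decision to abandon error control. But D.17 applies 0.05 to all analyses and mentions no per-scale level, so the plan as written does not implement it. The supplied SAP contains only D.17, and protocol 3.3.2.2 refers to a D.20 that was not supplied. The protocol's own analysis section nevertheless has the same gap.

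**The 8% to 14% is hypothetical.** This stands as a limit. A reader might infer that the trial's false-positive rate is 8% to 14%. The documents do not support that: no any-one-counts rule is stated, the correlations are assumed, and the three sized scales are not the stated primary.

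**The primary is defined only once.** A reader might infer two rival primaries from sections 3.2 and 3.4.2.1. The latter lists data streams and never uses the word primary. The supportable point is narrower: the one definition given is open-ended, and the power calculation covers scales other than HDRS.

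**Acute RSA is harmless.** Largely so. Planning at .01 and testing at .05 is conservative for sample size. It is a minor inconsistency.

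**This is a Phase 2 trial and these are supporting scales.** Section 4.5.2.9 does call it Phase 2. But 3.2 places mood and anxiety scales inside the primary, and 3.5.2 itself claims an adjustment.

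**Conclusion.** The concern holds in this form: the sample size assumes error control for Aim 1 that the analysis plan does not apply, and the primary is not closed. The disagreement between .02 and 0.05 is on the page, and the stated power confirms it.

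The size depends on a choice the documents leave open. It is 5% if HDRS alone is primary, and 8.4% to 14.3% if any one of the three sized scales counts, against 3.5% to 5.9% at .02. Even .02 slightly exceeds 5% in total for nearly independent tests, since 3 × .02 = .06.

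Testing at 0.05 rather than .02 costs no power; the consequence is type I error. A reader might also take the stated 81% as power for the yoga-versus-walking comparison. The documents do not support that, because f comes from a yoga-only change and the 81% is reproduced with a total of 35. The 20% to 22% approximation shows that the matter needs restating; it is not an estimate of the planned model's power.

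**What to change.** Before outcome data are analysed, amend SAP D.17 and protocol 3.2, 3.4.2.1, 3.5.1, 3.5.2 and 3.5.5:

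1. Name one primary. HDRS is the natural choice: it is named first in 3.2 and 3.4.2.1, and 3.3.2.8 has it rated by blinded investigators. Test its group-by-time contrast through week 12 at two-sided 0.05. If a multi-scale primary is intended, list its members and apply Holm or Bonferroni.
2. Replace the blanket 0.05 for the other Aim 1 scales with the adjusted level or procedure that 3.5.2 already claims. List the family, and say whether EIFI is one score or four subscales and whether PSQI is included.
3. As a minor consistency point, make the .01 in 3.5.5 and the analysis level agree.
4. Restate Aim 1 power for the two-group group-by-time test at the level actually used. Say what f represents, and give the assumed HDRS effect and within-subject correlation.

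**Cost.** Wording and one restated power calculation. The documents give no HDRS effect size, so one must be assumed and declared. Mood-scale claims will need smaller p-values. The RSA change needs no extra subjects. The restated power may be well below 81%, which is better known before the analysis than after it.

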3.3.2. Study Related Procedures

3.3.2.1. Instruments: The following reliable and valid instruments will be used during the screening interview to determine eligibility, and to monitor subjects during the interventions:

- (1) Structured Clinical Interview for DSM-5 (**SCID-5**) is a widely used valid psychiatric diagnostic instrument used to screen for Axis I disorders(66);
- (2) **Columbia Suicide Safety Rating Scale (C-SSRS)** is a clinically administered instrument to assess suicide risk(67);
- (3) **Physical Activity Recall (PAR)** is a widely used structured interview that yields a weekly record of physical activity using Metabolic Equivalents (METs), a method of assessing an individual's level of physical activity in a common unit that can be calculated from a variety of activities.(55) The PAR will be obtained each week of the intervention in the event physical activity becomes a confounding factor.
- (4) **Hamilton Rating Scale for Depression (HDRS)** is a 17-item clinician administered scale frequently used to evaluate the effectiveness of antidepressants being assessed for FDA approval(68);
- (5) **Beck Depression Inventory (BDI-II)** is a 21-item self-administered instrument designed for the assessment of depressive symptoms, with higher scores reflecting greater severity(69);
- (6) **Spielberger State-Trait Anxiety Inventory (STAI)** is a self-administered instrument designed for assessment of trait anxiety (STAI-Trait) and serial assessments of state anxiety (STAI-State) with higher scores indicating higher anxiety(56);
- (7) **Clinician Administered Posttraumatic Stress Scale (CAPS)** is the gold standard clinician administered assessment for PTSD(70);
- (8) **PTSD Check List – Civilian (PCL-C)** is a 17-item self-administered scale corresponding to Diagnostic and Statistical Manual of Mental Disorders (DSM) IV criteria for PTSD. Because not all Veterans have combat experience and not all trauma is from a military experience, the civilian version of the PCL will be used. The use of the CAPS and PCL-C will allow assessment of severity of PTSD symptoms, and if present, will be modeled in statistical analyses;
- (9) **Exercise-Induced Feeling Inventory (EIFI)** is a self-administered instrument designed to assess four distinct feeling states associated with bouts of physical activity: Revitalization, Tranquility, Positive Engagement, and Physical Exhaustion.(57)

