3.5. Analysis Plan

3.5.1. Data Management and Analysis Plan: The study statistician and Healthcare Specialist will be responsible under a contract for data management and statistical analysis for the project. The Healthcare team will convert the REDCap shell from an earlier study and provide the monitoring reports, create of the final database. The study statistician will oversee the statistical analysis with the help of the Healthcare Specialist. Descriptive statistics will be generated for baseline data and distributions between the yoga intervention and walking intervention will be compared using two-sample t-tests and chi-square or Fisher's exact tests to assess effectiveness of randomization. Descriptive statistics include means and standard deviations for continuous variables and group sizes and proportions for categorical variables. All analyses will be performed at the $\alpha = 0.05$ level of significance. Should groups have unequal distributions at baseline, relevant variables will be incorporated in subsequent linear models that will be used to examine intervention efficacy. In order to address the study aims of assessing the relative longitudinal change independent variables between yoga intervention and walking intervention groups over time, data will be collected at four time points, pre-randomization, and at weeks 4, 8, and 12. Mixed linear model analyses will be performed focusing on the group x time interaction for the primary effects to be statistically modeled. These analyses will allow for inclusion of data at differing numbers of time points per subject if needed. We will examine different within-subject correlation structures for our interaction model and determine the optimal structure by comparing Akaike information criteria (AIC) values. The correlation structure that yields the lowest AIC will be adopted. Subjects who change antidepressant medications during the study will be included in intent to treat analysis, but will be co-varied for medication changes. Potential cohort effects will be statistically addressed by controlling for group profiles, including group size, breakdown by sex of attendees, instructor, group parameters such as individual or group sessions, and group cohesion/overlap.

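### Baseline covariates are chosen by imbalance tests and the group x time test does not condition on baseline HDRS, so precision is lost and the primary model depends on the data

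*SAP*

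**What the plan says.** SAP D.17 and Protocol 3.5.1 (Data Management and Analysis Plan) carry the same rule.

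- **Baseline testing.** The arms are compared with "two-sample t-tests and chi-square or Fisher's exact tests to assess effectiveness of randomization".
- **Trigger.** "Should groups have unequal distributions at baseline, relevant variables will be incorporated in subsequent linear models". The text does not say which variables are relevant or what counts as unequal.
- **Role of the baseline outcome.** "data will be collected at four time points, pre-randomization, and at weeks 4, 8, and 12", so the pre-randomization value is a response.
- **Test.** "Mixed linear model analyses will be performed focusing on the group x time interaction for the primary effects to be statistically modeled".
- **Covariates with no imbalance trigger.** Subjects who change antidepressants stay in the intent-to-treat analysis "but will be co-varied for medication changes". For group composition, "Potential cohort effects will be statistically addressed by controlling for group profiles". Protocol 3.3.2.1 says that the CAPS and PCL-C "will allow assessment of severity of PTSD symptoms, and if present, will be modeled in statistical analyses", but neither it nor the SAP gives the form.

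Two related points are unsettled. Protocol 2.2.q speaks of stratifying randomization on current PTSD, but the randomization section (3.3.2.7) names no strata. Table 3 lists two HDRS assessments before randomization, at screening and before Scan 1. The list of instruments for the imaging sessions, given after the instrument descriptions, leaves HDRS out.

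**The concern.** After proper randomization, a significant baseline difference is a chance event. It says nothing about whether the variable predicts outcome, so it is a poor guide to what belongs in the model. The rule also leaves the final form of the primary model open until the data have been seen.

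The larger loss comes from how baseline HDRS is used. With baseline as a free response visit, the week-12 part of group x time is the difference between arms in mean change. That fixes the weight on baseline at 1, although the efficient weight is the regression slope. At stake is power in a trial planned around 70 completers.

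**Working it through.** **1. The plan's own power figures.** The documents contain no power calculation for HDRS. The nearest is Protocol 3.5.2 (n=35, f=0.281, alpha 0.02, 81% power, based on EIFI). A repeated-measures F test with lambda = f² x N x m/(1-r), m=2, N=35 in total and r=0.5 (assumed, not stated) gives lambda = 0.0790 x 35 x 2/0.5 = 11.05. Power is then 0.806 for one group and 0.805 for a two-group interaction, so the stated figure is reproduced. The GABA figures (3.5.3; 26 per arm, SD 0.06) also reproduce: 0.795 at r=0.65 and 0.856 at r=0.70, against 80% and 85% stated. Neither calculation takes credit for conditioning on baseline.

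**2. A depression-scale correlation from the documents.** Protocol 2.2.h gives Study 4 BDI-II (n=30): 26.2 (SD 7.4) at baseline, 8.0 (SD 6.4) at week 12, paired t = -12.5.

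- SD of change = 18.2 x √30/12.5 = 7.97.
- r = (7.4² + 6.4² - 7.97²)/(2 x 7.4 x 6.4) = 32.1/94.7 = 0.34.

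The only other stated correlation is 0.65, assumed for GABA.

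**3. Variance with and without conditioning.** With equal SDs, the variance per subject is 2σ²(1-r) for change and σ²(1-r²) with baseline as covariate or constrained equal. The ratio is (1+r)/2. Starting from 80% power at two-sided 0.05 (the sidedness is assumed), the new power is Φ(2.80/√ratio - 1.96).

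| r | variance ratio | 80% becomes |
|---|---|---|
| 0.30 | 0.65 | 93.5% |
| 0.34 | 0.67 | 92.8% |
| 0.50 | 0.75 | 89.9% |
| 0.65 | 0.825 | 87.0% |

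On the BDI-II scale with its actual, unequal SDs, the adjusted SD is 6.4 x √(1-0.34²) = 6.02 against 7.97. With 35 per arm, the difference detectable with 80% power is 2.80 x SD x √(2/35), which falls from 5.3 to 4.0 points. That is a variance ratio of 0.57, lower than 0.67 because the two SDs differ.

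**4. What the trigger recovers.** Simulation with 6,000 runs, 35 per arm and the effect set for about 80% power of the change contrast. The trigger switches to baseline adjustment only when the baseline outcome differs significantly.

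| r | change contrast | with trigger | always adjusted | type I error with trigger |
|---|---|---|---|---|
| 0.34 | 79.2% | 80.4% | 91.5% | 3.7% |
| 0.50 | 78.8% | 79.6% | 88.2% | 4.6% |
| 0.65 | 78.8% | 79.5% | 85.7% | 4.8% |

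**5. Other covariates in the planned model.** In 40 simulated four-visit data sets, adding a prognostic time-invariant main effect left the variance of the week-12 group x time term unchanged (ratio 1.000). With complete data, a variable brought in by the trigger as a main effect therefore does nothing for the tested contrast. Constraining the arms to be equal at baseline gave a ratio of 0.74. The within-subject correlation in that set-up was (0.5² + 0.58²)/(0.5² + 0.58² + 0.8²) = 0.48, for which (1+r)/2 is also 0.74.

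**6. Cost.** With 70 completers, k uninformative covariates inflate variance by about 67/(67-k): 3% for k=2, 8% for k=5 and 17% for k=10.

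**The case against.** The strongest reply is that the plan already uses baseline HDRS, adjusts for several things without any trigger, and keeps its error rate. Much of this stands.

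- **A reader might infer that baseline HDRS is left out.** It is in the model as a response visit. The loss comes from not conditioning on it or constraining it.
- **A reader might infer that covariates enter only after an imbalance.** Medication changes and group profiles enter regardless, but they arise after randomization and cannot stand in for baseline adjustment. PTSD severity is to be modeled if present, so PTSD is not ignored, though its form is unspecified. Baseline antidepressant use has its own exploratory hypothesis (4a).
- **A reader might infer that the result would be invalid.** The simulated type I error was 3.7% to 4.8%, so no inflation was found.
- **A reader might infer that adding prognostic factors is a free gain.** In the planned model, main effects add nothing to group x time, and uninformative covariates cost precision. The documents give no prognostic effect or prevalence for PTSD from which to calculate a gain.

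The reply leaves the main point standing: the tested contrast carries the variance of a change score, and the trigger hardly alters that.

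**Conclusion.** The concern holds as a matter of precision and prespecification, not of bias or false-positive risk. Conditioning on baseline would cut the variance of the week-12 comparison by 17.5% to 35% for r from 0.65 to 0.3, and the trigger adds only about one percentage point of power.

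The size rests on three assumptions: that group x time is fitted without a baseline constraint, which is the natural reading; that SDs are similar at the two visits; and that r lies in the stated range. The HDRS value is unknown. The BDI-II figure of 0.34 comes from a single study of 30 people, all given yoga. The HDRS entry threshold of 14 would tend to lower r, towards the end where the saving is larger. The direction does not depend on r: the regression slope minimizes the variance, and a change score fixes that slope at 1.

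**What to change.** In SAP D.17 and Protocol 3.5.1:

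1. Delete the baseline-test trigger and report baseline data descriptively.
2. Prespecify one model: either (a) HDRS at weeks 4, 8 and 12 with group, time, group x time and baseline HDRS x time, or (b) a four-visit model with arm means constrained equal at baseline.
3. Name the between-arm difference at week 12 as the primary contrast. This is essential under (a): once baseline leaves the response, group x time asks only whether the arm difference varies over weeks 4, 8 and 12, and would miss a constant benefit present from week 4.
4. State whether the screening or the pre-Scan 1 HDRS is the baseline, and reconcile Table 3 with the imaging-session instrument list.
5. Reconcile Protocol 2.2.q with 3.3.2.7 on PTSD stratification. If PTSD is a stratifier, include it as a prespecified covariate in a form consistent with 3.3.2.1.

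The cost is a change to the text, including the definition of the primary contrast, and a few degrees of freedom: about 3% variance inflation for two uninformative covariates. No further data collection is needed.
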